### Quality of life

The FACT-Hep will be utilized to assess quality of life at the pre-determined time intervals specified above. Longitudinal measurements of FACT-Hep scores will be modeled using mixed effects linear regression. Randomization assignment, time, and randomization by time interaction terms will be included in the model as fixed effects. An appropriate

correlation structure will be assumed for the residual covariance matrix to account for within-subject correlation. Groups will be compared with respect to average scores at 12 weeks using a linear contrast of model parameters. Missing data will not be imputed for this analysis.

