#### **Secondary:**

The secondary outcome measures will include:

- Quality of life, as measured by the FACT-Hep total score, and FACT-Hep subscores.
- Measurements of overall survival

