### **3.1 Study Characteristics**

Patients may be non-depressed or depressed. Those who are severely depressed according to the Quick Inventory of Depression Survey (QIDS  $\geq 16$  points) will be referred to a psychiatrist for further evaluation and possibly additional therapy, based on clinical judgement. The study will be started at University Hospitals Cleveland Medical Center with the possibility that it can be opened at alternative sites if needed for patient accrual.

At the time of study enrollment, the treating physician must have the intent to treat the patient with 12 weeks of neoadjuvant chemotherapy as standard of care cancer treatment. For this study, patients will be randomized in a 1:1 ratio to receive escitalopram or placebo using a randomization table prepared by the study statistician. This randomization table will be shared by the statistician only with the Investigational Drug Services Pharmacy (IDS) personnel and will detail for all 55 patients/study IDs whether that patient is to receive escitalopram or placebo. Each patient will be

assigned a study number, in sequential order, only after all eligibility criteria have been confirmed by the study coordinator, treating physician (Investigator or Co-investigator) involved in the case, and by a member of the Clinical Trials Unit's Quality Assurance department.

It is possible that burden of disease could influence mood. Therefore, patients will also be stratified according to whether they have resectable disease or locally advanced disease (borderline resectable or unresectable) according to NCCN criteria. A pancreatic surgeon (PI or Co-Investigator) will determine this status using the Tumor Profile Assessment (see Appendix VIII). The Tumor Profile Assessment is to be filled out by the PI or by the Co-investigator prior to randomization.

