### **3.2 Number of Subjects**

The clinical trial is powered for 46 patients, including 23 patients in each arm (escitalopram and placebo). However, 55 patients will be enrolled, in order to achieve the desired number due to expected attrition both before and after initiation of therapy or due to removal from study due to reasons noted in Section 6.2.

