There will be study-related clinic visits scheduled for Days 15 and 71. On Day 15, patients will be given pill bottles for Weeks 3-10. On Day 71, patients will be given pill bottles for Weeks 11-12. The Week 11-12 pill diary along with any unused pills will be collected at the end of treatment clinic visit (Week 13, Day 85). All other visits will be conducted via phone call from the study staff every two weeks beginning on Day 8. Phone visits will be conducted on Days 8, 22, 36, 50, 64 and 78 (+/- 7 days). However, if a patient's scheduled chemotherapy-related visit, clinic visit or hospital visit for any other reason happens to fall on (or within the 7 day window of) a planned study visit, the visit may be conducted in person with study staff. During these visits (phone or in-person), the study staff will perform a toxicity assessment and ask questions to determine if the patient is being compliant with taking the pills and completing the pill diary. The study staff member will verbally conduct the QIDS-SR, PHQ-9, and FIBSER with the patient and record the patient's answers and the FACT-Hep will be given directly to the patient to complete (if not done over the phone). The FACT-Hep will be performed monthly on Days 1, 22, 50 78, and 85.

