### Depression

The primary outcome is moderate or greater depression defined as a QIDS-SR score greater than 11. All patients will have localized disease, but be stratified by extent of disease: resectable vs. unresectable, based on imaging and as determined by the PI Based on the Tumor Profile Assessment. Under Generalized Linear Model (GLM) framework, a modified Poisson model can be constructed as the working model to directly estimate the relative risk of depression at each measurement time through 12 weeks (Zou and Donner 2013). Measurement time will be treated as a categorical/ordinal variable to allow for differing risk of depression in controls at each time point. The model will adjust for baseline QIDS-SR score as a continuous covariate and the stratification variable. Generalized Estimating Equation (GEE) will be used to account for correlation among the 6 repeated post-randomization measurements through month 3 for each participant. A time by randomization assignment interaction variable will be included to allow for estimation of the relative risk at each measurement time. The primary interest is to compare the two treatment groups at 12 weeks. This comparison will be performed at the one-sided alpha=0.10 level.

Since the GEE estimates are only valid under the Missing At Random (MAR) assumption if the working correlation structure is correctly specified, missing dichotomous outcomes will be imputed using Multiple Imputation (MI) prior to analysis (Li et al 2006). Estimates using this method are consistent under the MAR assumption (Beunckens et al 2008).

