### **Survival**

Overall survival will be measured from the date of randomization to date of death or last follow-up, and adjusted for staging. The distribution of survival time will be estimated using the Kaplan-Meier method, and randomization groups will be compared using a stratified log-rank test.

The primary and secondary analyses will be performed on all randomized patients. Patients will be analyzed according to randomization assignment, regardless of the treatment actually received.

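### The FACT-Hep mixed model does not adjust for the Day 1 score or the resectability stratum, so its 12-week comparison is valid but less precise than it could be

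*Combined protocol and SAP*

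**What the plan says.** Section 2.4 lists among the secondary measures "Quality of life, as measured by the FACT-Hep total score, and FACT-Hep subscores". Section 6.1 sets the schedule: "The FACT-Hep will be performed monthly on Days 1, 22, 50 78, and 85". The screening list in section 11.1.1 and the study calendar also place a FACT-Hep on Day 1, and there is a further one at Week 25.

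For the analysis, section 14.2 (Quality of life) proposes a linear mixed model for the repeated scores: "Randomization assignment, time, and randomization by time interaction terms will be included in the model as fixed effects". The comparison is then defined: "Groups will be compared with respect to average scores at 12 weeks using a linear contrast of model parameters". The residual covariance is left open, time is not described as categorical or continuous, and missing scores are not imputed. No section adds baseline FACT-Hep or the stratification factor to this model.

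The primary analysis in the same section is specified differently. For QIDS, time is categorical, and "The model will adjust for baseline QIDS-SR score as a continuous covariate and the stratification variable".

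**The concern.** A longitudinal mixed model can look as if it uses the baseline simply because Day 1 is one of its visits. With an arm effect, visit effects and their interaction, however, each arm has its own free mean at every visit, Day 1 included. The model is never told that randomization makes the Day 1 means equal in expectation. The Day 1 score is therefore not used to sharpen the 12-week difference, and a chance Day 1 gap passes into that difference in proportion to the correlation between the two scores.

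The contrast is unbiased under randomization and the test keeps its level. At stake is the precision of a listed secondary outcome in a trial with about 23 patients per arm, and the plan gives no reason for treating it differently from the primary.

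**Working it through.** **Inputs from the documents.** 23 per arm at 12 weeks, 55 randomized (about 27 per arm) and up to 15% attrition (14.3); FACT-Hep on Days 1, 22, 50, 78 and 85 (6.1); fixed effects and contrast (14.2).

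**Assumptions.** The documents give no FACT-Hep SD, correlation or alpha. The SD is set to 1 at each visit, the baseline-to-12-week correlation ρ to 0.3, 0.5 and 0.7, and visit is categorical unless stated.

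**1. The plan's own power figure.** There is none for FACT-Hep. The only one is for QIDS: 23 per arm, 40% vs 13.8%, one-sided 0.10, 80% power. The unpooled normal formula gives Φ(0.262/√(0.40×0.60/23 + 0.138×0.862/23) − 1.2816) = 79.3%. The exact binomial power of the pooled z-test is 80.1%. Also, 46/0.85 = 54.1, rounded up to 55. The figures reproduce; they serve here only to fix n.

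**2. The planned contrast.** The generalized least squares variance was computed for the five visits with complete data. The 12-week contrast has variance 2/23, exactly that of the raw 12-week difference (ratio 1.000), under both compound-symmetry and exponential-decay correlation.

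**3. With baseline adjustment or a common Day 1 mean.** The variance becomes (2/23)(1 − ρ²). Estimating the slope in a covariate model multiplies this by 1 + 1/(46 − 4). Differences detectable with 80% power are (z + 0.8416)·√((2/23)(1 − ρ²)), with z = 1.9600 for two-sided 0.05 and 1.2816 for one-sided 0.10 (the primary's level, borrowed).

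| | Variance ratio | With slope penalty | SE reduction | Equivalent n per arm, 23/(1 − ρ²) | Detectable, two-sided 0.05 | Detectable, one-sided 0.10 |
|---|---|---|---|---|---|---|
| Planned | 1 | – | – | 23 | 0.83 SD | 0.63 SD |
| ρ = 0.3 | 0.91 | 0.93 | 5% | 25.3 | 0.79 SD | 0.60 SD |
| ρ = 0.5 | 0.75 | 0.77 | 13% | 30.7 | 0.72 SD | 0.54 SD |
| ρ = 0.7 | 0.51 | 0.52 | 29% | 45.1 | 0.59 SD | 0.45 SD |

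After the slope penalty the equivalent n is 24.7, 30.0 and 44.0. A simulation of 40,000 trials gave variance ratios of 0.927, 0.772 and 0.525.

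**4. With dropout.** Take 27 per arm, 15% random dropout and compound symmetry. Under the planned model the earlier visits recover a little from dropouts: its variance is 0.99, 0.95 and 0.92 of the completers-only variance. The common-baseline model still has only 0.92, 0.78 and 0.55 of the planned model's variance.

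**5. If time is linear.** Day 1 then helps through the slope. The planned variance is 0.63–0.84 of the raw 12-week variance under compound symmetry and 0.98–1.00 under decay. A common baseline lowers it further, to 0.91, 0.69 and 0.42 of the planned value (compound symmetry) or 0.92, 0.75 and 0.51 (decay).

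**6. Validity and power.** In 4,000 simulated trials at two-sided 5%, type I error without adjustment was 5.2% (ρ = 0.5) and 5.0% (ρ = 0.7); with adjustment it was 5.4% and 5.8%. The Monte Carlo SE is √(0.05×0.95/4000) = 0.34 points. The adjusted t-test is exact for the normal data simulated, so the 5.8% is simulation noise. Power at 0.8 SD rose from 75.6% to 85.3% (ρ = 0.5) and from 75.4% to 95.1% (ρ = 0.7).

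**7. Chance imbalance.** The Day 1 gap has SD √(2/23) = 0.295. Multiplied by ρ, it carries 0.09, 0.15 or 0.21 SD into the 12-week difference.

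**8. The stratum.** If it explains 2%, 5% or 10% of the variance, the SE falls by 1 − √(1 − R²) = 1.0%, 2.5% or 5.1%.

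**The case against.** The best reply is that nothing here is wrong. The comparison is unbiased, FACT-Hep carries no alpha, power or sample-size claim, and a phase II trial seeking preliminary evidence may choose a simpler model. The gain depends on a correlation the documents do not give; with chemotherapy between the two measurements it could be as low as 0.3, where the SE falls by only about 3–5%. This stands. It limits the point to an improvement of unknown but non-negative expected size, apart from the small slope penalty.

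Other points have some force:

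- Lost precision and exposure to chance imbalance are one loss, not two. The squared carry-over ρ²×2/23 (0.0078, 0.0217, 0.0426) is exactly the variance that adjustment removes. This is correct, and the two should not be added.
- The text says the three terms will be included, not that they are the only ones. Set beside the explicit covariates in the QIDS paragraph, omission is still the natural reading.
- Time is not stated to be categorical. Step 5 shows that a common baseline helps in either case.
- Keeping patients without a Day 1 score is a limited benefit. Section 3.2 enrols 55 patients "due to expected attrition both before and after initiation of therapy", but those lost before therapy will mostly have no later score either.
- The common-mean constraint needs the Day 1 form to precede the first dose, and section 6.1 expressly places only the blood draw there. The practical effect is probably negligible, but the condition should be stated.
- An unstructured covariance has 15 parameters with five visits and 21 with Week 25, which is heavy for 46 patients. Hence the need for a fallback.

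**Conclusion.** The concern holds as a loss of precision, not as bias or an invalid test. As written, the FACT-Hep contrast makes little use of a baseline the trial already collects, and none with categorical visits and complete data. The recoverable share of the variance is 9%, 25% or 49% at correlations of 0.3, 0.5 or 0.7, or roughly 7%, 23% or 48% after estimating a slope. These figures assume equal variances across visits and 23 per arm. The correlation is the decisive unknown. The stratum adds little precision and belongs in the model mainly for consistency with the design. The change should be made, but the trial's primary conclusion does not depend on it.

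**What to change.** In section 14.2 (Quality of life):

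1. State that visit is categorical, which of Day 78 and Day 85 is the 12-week visit (their ±7-day windows overlap), and whether Week 25 enters the model.
2. Include the Day 1 FACT-Hep as a response with its mean constrained equal across arms, counting it as baseline when completed before the first dose. This fits the rule that "The primary and secondary analyses will be performed on all randomized patients". Alternatively, add baseline FACT-Hep and baseline-by-visit as fixed effects and say how patients without a baseline are handled.
3. Add the resectability stratum as randomized in section 3.1, which groups borderline with unresectable disease. The depression paragraph words it as resectable against unresectable; use one definition throughout.
4. Name an unstructured covariance, with a prespecified simpler structure if it does not converge.

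The cost is a few sentences and somewhat more model specification. No new data, visits or patients are required. Settling this before unblinding also removes a later choice between adjusted and unadjusted results. The covariate version drops anyone without a Day 1 score; the constrained version does not.

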### **Survival**

Overall survival will be measured from the date of randomization to date of death or last follow-up, and adjusted for staging. The distribution of survival time will be estimated using the Kaplan-Meier method, and randomization groups will be compared using a stratified log-rank test.

The primary and secondary analyses will be performed on all randomized patients. Patients will be analyzed according to randomization assignment, regardless of the treatment actually received.

### **Treatment failures**

Patients with high risk for suicide, suicide attempts, or a score of  $\geq 16$  points on the QIDS-SR at 12 weeks will be considered “treatment failures” and will be provided referrals for more optimal depression treatment throughout the duration of the study. Patient scores and adverse events will be reviewed by clinical study staff (RN or MD) within 24 hours of collecting information from patients to determine if additional action is needed per Section 7. Cases of suspected suicidal ideation will be reviewed within four hours as noted in Section 7, and study staff will immediately take action as appropriate upon review.

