## **6.2 Criteria for Removal from Study**

### **Withdrawal Visit/Discontinuation of Therapy**

In the absence of treatment delays due to adverse events, treatment may continue for 12 weeks or until one of the following criteria applies:

- Patient misses more than four consecutive weeks of escitalopram.
- Intercurrent illness that prevents further administration of treatment or patient inability to swallow escitalopram/placebo capsules,
- The investigator considers it, for safety reasons, to be in the best interest of the patient.
- Unacceptable adverse event(s):

-NCI CTCAE version 5.0 Grade 2 or higher hemorrhage that occurs within the first four weeks of treatment  
-NCI CTCAE version 5.0 Grade 4 suicidal ideation  
-NCI CTCAE version 5.0 Grade 3 or higher mania  
-NCI CTCAE version 5.0 Grade 4 hyponatremia

Patients who experience severe depression will be referred to a psychiatrist. They will also continue, if agreeable, on the study and with scheduled surveys according to the defined schedule (QIDS, PHQ-9, FACT-Hep, FIBSER).

Patients will be withdrawn if they are deemed at high risk for suicide or if they wish to voluntarily withdraw from the study.

- Patient decision to withdraw from treatment (partial consent) or from the study (full consent),
- Pregnancy during the course of the study
- Death

- The Principal Investigator and/or the Case Comprehensive Cancer Center Data Safety Toxicity Committee (DSTC) reserve the right to temporarily suspend or prematurely discontinue this study if unacceptable study-related risks are identified. The date and reason for discontinuation must be documented. Every effort should be made to complete the appropriate assessments.

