**Table 7.1 Criteria for dosing delays and re-initiation of treatment due to study drug-related toxicity**

CTCAE Grade* Patient report or from any assessment scale	Dose Discontinuation Guidelines	
Hemorrhage (any site)	Grade 1: Mild symptoms; intervention not indicated Grade 2: Moderate symptoms; intervention indicated Grade 3: Transfusion indicated; invasive intervention indicated; hospitalization Grade 4: Life-threatening consequences; urgent intervention indicated	Grade 2 or greater: Discontinue drug, inform treating physician and PI immediately upon discovery.  (if this happens within first 4 weeks remove patient from study)
Suicidal ideation**	Grade 1: Increased thoughts of death but no wish to kill oneself Grade 2: Suicidal ideation with no specific plan or intent Grade 3: Specific plan to commit suicide without serious intent to die which may not require hospitalization Grade 4: Specific plan to commit suicide with serious intent to die which requires hospitalization	Grade 1-3: inform treating physician immediately upon discovery Grade 4: discontinue drug and remove from study.  See Table 7.2
Mania	Grade 1: Mild manic symptoms (e.g., elevated mood, rapid thoughts, rapid speech, decreased need for sleep) Grade 2: Moderate manic symptoms (e.g., relationship and work difficulties; poor hygiene)	Grade 3-4: discontinue drug and remove from study, notify treating physician and PI immediately.

	Grade 3: Severe manic symptoms (e.g., hypomania; major sexual or financial indiscretions); hospitalization not indicated; new onset  Grade 4: Life-threatening consequences, threats of harm to self or others; hospitalization indicated	
Hyponatremia	Grade 1: <LLN - 130.0 mmol/L  Grade 2: 125-129 mmol/L and asymptomatic  Grade 3: 125-129 mmol/L symptomatic; 120-124 mmol/L regardless of symptoms  Grade 4: <120 mmol/L; life-threatening consequences	Grade 4: discontinue drug and remove from study.
*CTCAE Version 5.0		
**Please see safety guidelines section below regarding patients exhibiting suicidal ideation		

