### Safety Assessment

Patients will not be allowed to participate or will be withdrawn if at any point in the trial they are found to be at high risk for suicide. Patients who provide an affirmative response (checks 1, 2 or 3) on Question 12 of QIDS will be referred and evaluated by a UH/Seidman Psychiatrist to assess whether high risk for suicide is present. Patients who are severely or moderately severely depressed by QIDS ( $\geq 16$ ) or PHQ-9 greater than 14 will be referred and evaluated by a UH/Seidman psychiatrist. They will not be discontinued from the trial, but may be offered additional therapy as part of standard of care, according to the judgement of the evaluating psychiatrist.

For a referral to a Psycho-Oncology Provider call [REDACTED] or email [REDACTED], [REDACTED]

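### Patients with no 12-week QIDS-SR after suicide-related withdrawal or a suicide attempt are labelled treatment failures, but the primary analysis imputes them under MAR

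*Combined protocol and SAP*

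**What the plan says.** Section 14.2, under Depression, sets a single criterion: "The primary outcome is moderate or greater depression defined as a QIDS-SR score greater than 11". The comparison of interest is at 12 weeks. In the same place, "missing dichotomous outcomes will be imputed using Multiple Imputation (MI) prior to analysis", with the justification "Estimates using this method are consistent under the MAR assumption". The variables in the imputation model are not listed, and no analysis under a different missing-data assumption is planned.

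Further on, Section 14.2 defines treatment failures as "Patients with high risk for suicide, suicide attempts, or a score of" 16 or more on the QIDS-SR at 12 weeks. The stated consequences are referral and prompt staff review. The label appears in no model or endpoint.

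Three places take such patients off the trial:
- Section 6.2: "Patients will be withdrawn if they are deemed at high risk for suicide or if they wish to voluntarily withdraw from the study".
- Section 7.0, Safety Assessment: patients "will be withdrawn if at any point in the trial they are found to be at high risk for suicide".
- Table 7.1, suicidal ideation row: "Grade 4: discontinue drug and remove from study". (The hyponatremia row carries the same instruction.)

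A suicide attempt is not itself named as a withdrawal criterion.

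Follow-up after withdrawal is described inconsistently. Section 6.1 (Unblinding Procedures), Section 6.2 (handling of withdrawals) and the last paragraph of Section 7.0 keep questionnaires going. The preceding paragraph of Section 7.0 says that patients whose event falls in the first four weeks are removed and not followed. Section 14.3 makes a serious adverse event that stops the drug in that window a reason to call the patient not evaluable and to replace them. Section 14.2 (end of Survival) analyses everyone randomized. Section 3.3 and the Replacement Policy in Section 14.3 rule out replacement.

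**The concern.** The analysis plan names a class of patients as failures and then gives them no role in the analysis. For those who leave without a 12-week score, the outcome is a random draw under MAR. MAR is hard to defend here. The exit is triggered by suicidality, which is item 12 of the QIDS-SR, and by a psychiatrist's judgement that is not among the variables the plan mentions. Earlier QIDS-SR scores would help if they are in the imputation model, but they cannot capture a deterioration between surveys.

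The direction of the bias depends on the arm. Suicide-related losses on placebo that are drawn as not depressed hide placebo failures and cost power. The same losses on escitalopram make the drug look better and hide possible harm. The trial enrols patients whatever their depression score, including severe depression, so such events are foreseeable. Each patient is unblinded at Day 85, so a rule chosen late could be chosen with knowledge of the arm.

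**Working it through.** **Inputs from Section 14.3.** 23 per arm; true rates 40% (placebo) and 13.8% (escitalopram); one-sided alpha 0.10; stated power 80%.

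**Inputs not in the documents (assumed).** f is the fraction of an arm that leaves for suicide-related reasons with no 12-week score. All of these patients are taken to be true events. q is the probability that imputation draws them as depressed, taken as 0.5 to 0.9. The apparent event rate in an affected arm is then: true rate − f × (1 − q).

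**1. Reproduce the plan's power.** Unpooled normal approximation: SE = √(0.4×0.6/23 + 0.138×0.862/23) = 0.125. Then 0.262/0.125 = 2.10, minus 1.28 gives 0.82, and Φ(0.82) is about 79.3%. Exact enumeration of the two binomials with a pooled z-test gives 80.1%. Both agree with the stated 80%, and the exact calculation is used below.

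**2. Placebo only, f = 8% (0.08 × 23 = 1.84, about two patients).**
- q = 0.5: 0.40 − 0.08×0.5 = 0.360, power 71%.
- q = 0.7: 0.40 − 0.08×0.3 = 0.376, power 75%.
- q = 0.9: 0.40 − 0.08×0.1 = 0.392, power 78%.

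**3. Escitalopram only, f = 4% (0.04 × 23 = 0.92, about one patient).**
- q = 0.5: 0.138 − 0.04×0.5 = 0.118, chance of a positive result 85%.
- q = 0.7: 0.138 − 0.04×0.3 = 0.126, chance of a positive result 83%.

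**4. One patient in each arm (f = 4% in both).**
- q = 0.5: 0.380 v 0.118, power 82%.
- q = 0.7: 0.388 v 0.126, power 81%.
- q = 0 (none drawn as depressed): 0.360 v 0.098, power 83%.

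The change from 80% is about 1 to 3 points.

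**5. Effect on one result.** Start from counts near the design rates, placebo 9/23 and escitalopram 3/23, and recount escitalopram non-events as events (pooled z, one-sided).
- 3/23: p = 0.022.
- 4/23: p = 0.051.
- 5/23: p = 0.09997, still below 0.10.
- 6/23: p = 0.173.

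Three recounted escitalopram patients are needed to lose significance from this starting point.

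These figures are illustrations. They use a two-proportion test with a single draw per missing patient, not the planned covariate-adjusted modified Poisson GEE with multiple imputation.

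**The case against.** The strongest reply is that the plan already follows a coherent treatment-policy approach. Questionnaires generally continue after the drug is stopped, all randomized patients are analysed, and the question is depression at 12 weeks. A patient at high risk in week 4 who scores 6 in week 12 is not depressed at week 12, and using that score is not misclassification. This stands: overriding an observed score would be a choice of a different estimand, so it belongs in a sensitivity analysis.

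It can also be said that the Treatment failures paragraph is really a referral rule, and that renaming or moving it would remove the mismatch. That would tidy the label, but the missing 12-week values would still be imputed under an implausible assumption.

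Imputation also does not set anyone to not depressed. With the biweekly QIDS-SR history in the model, the draw could favour depressed strongly, and the loss shrinks as q approaches 0.9. That is fair, but the plan does not say which variables enter the model.

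Finally, the assumed 8% and 4% have no source in the documents, and one-sided scenarios exaggerate the effect compared with a balanced one. This also stands, and it is why the size is given as a range that includes the balanced case.

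**Conclusion.** The gap is real but narrow. It covers randomized patients with no 12-week QIDS-SR after withdrawal or removal for high suicide risk or Grade 4 suicidal ideation, or after a suicide attempt. The plan calls the high-risk and attempt cases failures, yet leaves all these outcomes to a MAR draw. Few patients are likely to be affected. Under the assumptions above, power moves from 80% to about 71-78% if about two placebo patients and no escitalopram patients are affected. It changes by about 1 to 3 points if one patient per arm is affected. The bias can go either way.

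A reader might infer three stronger things that the documents do not support:
- That all treatment failures escape the primary endpoint. A QIDS-SR of 16 or more at 12 weeks exceeds the cut-off and is already an event, and so is any other observed score above it.
- That the plan scores its worst outcomes as successes. Imputation gives a probability, and an observed score at or below the cut-off is a valid 12-week outcome.
- That a single patient would overturn the trial. From a design-like result it takes three; one matters only when the result already sits at the boundary.

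The point deserves a sentence in the plan before any data are unblinded. It does not undermine the design.

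**What to change.** In Section 14.2, state that a randomized patient with no 12-week QIDS-SR after withdrawal or removal for high suicide risk or Grade 4 suicidal ideation, or after a suicide attempt (withdrawn or not), counts as an event in the primary analysis and is not imputed under MAR. Keep every observed 12-week score as observed. Report the number of such patients by arm.

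Add two sensitivity analyses: one in which these patients are imputed under MAR as now planned, and one composite in which all patients with these suicide-related events count as events whatever their 12-week score.

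Reconcile the no-follow-up statement in Section 7.0 and the not-evaluable-and-replaced rule in Section 14.3 with the all-randomized analysis in Section 14.2 and the no-replacement statements in Sections 3.3 and 14.3. Early suicide-related removals should not drop out of the analysis by default.

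The cost is plan wording and one derived variable. The downside is an endpoint that becomes slightly composite in a few patients. No clinical rule needs to change for the coding itself.
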